Summary Table of Study Protocol

Title	An Observational Case Series to Describe Women Exposed to Repatha During Pregnancy and Infant Outcomes During the First Year of Life
Protocol version identifier	20200408, 1.0
Date of last version of the protocol	03 March 2021
EU Post Authorization Study (PAS) Register No	TBD (Registration will occur after approval of the protocol and prior to commencement of first data capture)
Active Substance	Evolocumab
Medicinal Product	Repatha
Device	NA
Product Reference	NA
Procedure Number	NA
Joint PASS	Yes
Research Question and Objectives	Among women exposed to Repatha during pregnancy, to estimate the proportion of: 
- pregnancy and maternal complications- adverse events in the developing fetus and neonate- and among their infants, adverse events for the first year of life.
Country(ies) of Study	Global

Author	PPD [REDACTED], Manager, Observational Research, Amgen Inc., [name] PPD [REDACTED]
	PPD [REDACTED], Director, Observational Research, Amgen Inc., [name] PPD [REDACTED]
	PPD [REDACTED], Director, Global Safety, Amgen Inc., [name] PPD [REDACTED]
	PPD [REDACTED], Director, Regulatory Affairs, Amgen Inc., [name] PPD [REDACTED]
	PPD [REDACTED], Medical Director, Clinical Research, Amgen Inc., [name] PPD [REDACTED]

Marketing Authorization Holder

Marketing authorization holder(s)	Amgen Inc.
MAH Contact	PPD [REDACTED], Regulatory Affairs Manager, Amgen Inc., [name] PPD [REDACTED]

This protocol was developed, reviewed, and approved in accordance with Amgen's standard operating procedures.

Confidentiality Notice

This document contains confidential information of Amgen Inc.

[figure not shown]
This document must not be disclosed to anyone other than the site study staff and members of the Institutional Review Board/Independent Ethics Committee/Institutional Scientific Review Board or equivalent, as applicable.

The information in this document cannot be used for any purpose other than the evaluation or conduct of the research without the prior written consent of Amgen Inc.

If you have questions regarding how this document may be used or shared, call the Amgen Medical Information number: Amgen's general number in the US ([name]).

12.	Plans for Disseminating and Communicating Study Results	23
12.1	Publication Policy	23
13.	References	24
14.	Appendices.....	25

List of Appendices

Appendix A.	List of Stand-alone Documents.....	26
Appendix B.	ENCePP Checklist for Study Protocols.....	27
Appendix C.	Initial Pregnancy Questionnaire – Mother	34
Appendix D.	6 to 8 Weeks Post Due Date Questionnaire – Mother	38
Appendix E.	6- and 12-month Infant Questionnaire	40

2. List of Abbreviations

Acronym	Definition
AGS	Amgen Global Safety
ENCePP	European Network of Centres for Pharmacoepidemiology and Pharmacovigilance
EU	European Union
FDA	Food and Drug Administration
HCP	Healthcare provider
HIPAA	Health Insurance Portability and Accountability Act
HeFH	Heterozygous Familial Hypercholesterolemia
HoFH	Homozygous Familial Hypercholesterolemia
IEC	Independent Ethics Committee
IRB	Institutional Review Board
LDL	Low-Density Lipoprotein
LDL-C	Low-Density Lipoprotein Cholesterol
LMP	Last menstrual period
MAH	Marketing Application Holder
MI	Myocardial Infarction
OTC	Over the counter
PASS	Post-authorisation safety study
PCSK9	Proprotein Convertase Subtilisin Kexin type 9
PCSK9i	Proprotein Convertase Subtilisin Kexin type 9 inhibitor
US	United States
USPI	United States Prescribing Information

3. Responsible Parties

PPD [REDACTED], PhD, MPH, Amgen Inc.

PPD [REDACTED], PhD, MPH, Amgen Inc.

PPD [REDACTED], RN, Amgen Inc.

PPD [REDACTED], MS, RAC, Amgen Inc.

PPD [REDACTED], MD, Amgen Inc.

4. Abstract

- Study Title

An Observational Case Series to Describe Women Exposed to Repatha During Pregnancy and Infant Outcomes During the First Year of Life

- Study Background and Rationale

Repatha is a proprotein convertase subtilisin kexin type 9 inhibitor (PCSK9i) antibody indicated to (1) reduce the risk of myocardial infarction (MI), stroke and coronary revascularization in adults with established cardiovascular disease (2) as an adjunct to diet, alone or in combination with other lipid-lowering therapies (eg, statins, ezetimibe), for treatment of adults with primary hyperlipidemia (including heterozygous familial hypercholesterolemia [HeFH]) to reduce low-density lipoprotein cholesterol (LDL-C) and (3) as an adjunct to diet and other LDL-C lowering therapies in patients with homozygous familial hypercholesterolemia (HoFH) who require additional lowering of LDL-C.

This study is being conducted to address a Food and Drug Administration (FDA) postmarketing requirement to conduct a single-arm prospective and retrospective observational study of pregnant women exposed to Repatha to evaluate fetal and infant outcomes through the first year of life. This study will estimate the proportion of pregnancy and maternal complications, adverse events in the developing fetus and neonate, and adverse events in the infant through the first year of life using data from pre-existing reports within Amgen's Global Safety Database.

- Research Question and Objective(s)

Objectives	Endpoints
Primary	
Among women exposed to Repatha during pregnancy, to estimate the proportion of: 
- Pregnancy and maternal complications- Adverse events in the developing fetus and neonate- And among their infants, adverse events for the first year of life.	
• Number of cases reporting pregnancy and maternal complications.• Pregnancy Outcomes: Number of cases reporting live full-term births, spontaneous abortion, elective abortion, stillbirth, and premature delivery.• Infant Outcomes: Number of cases reporting adverse events including complications, medical problems or congenital anomalies at birth.• Number of cases reporting adverse events at 6 months and 12 months.

- Hypothesis(es)/Estimation

This is an estimation study. No formal hypothesis will be tested.

- Study Design/Type

This is a Global prospective and retrospective observational case series of pregnant women exposed to Repatha during pregnancy and their infants through the first year of life.

- Study Population or Data Resource

Case finding through the Amgen Global Safety Database and other post marketing sources which include: spontaneous (including regulatory authority and literature), solicited (ie, patient support programs and market research), and postmarketing non-interventional studies. Retrospectively, data will be extracted from pre-existing postmarketing reports obtained from Amgen's Global Safety Database for women exposed to Repatha during pregnancy and their infants between July 2015 and the approval date of this protocol. Prospectively, from approval date of this protocol through July 2025, secondary data from postmarketing reports will be analyzed for women who have been exposed to Repatha during their pregnancy and their infants. Patients who refused consent will be excluded.

- Summary of Patient Eligibility Criteria

Women exposed to Repatha during pregnancy and their infants through the first year of life who consent to provide their information to Amgen.

- Follow-up

If the pregnant women consent for follow-up, then Amgen will follow-up with the pregnant women from the time they are exposed to Repatha through the pregnancy outcome and their infants will be followed through the first year of life.

- Variables

Outcome Variable(s): The outcomes for the study include occurrence and dates of pregnancy and maternal complications, pregnancy outcomes, and infant outcomes based on self-report. Pregnancy outcomes include the number of cases reporting live full-term births, spontaneous abortion, elective abortion, fetal death/stillbirth, and premature delivery. Infant outcomes are the number of cases reporting adverse events including complications, medical problems or congenital anomalies at birth and the number of cases reporting adverse events at 6 months and 12 months which may include whether they have not followed growth curves or met development milestones as expected for chronological age.

Exposure Variable(s): The period defining exposure to Repatha during pregnancy will be any number of days, at any dose, and at any time from up to 90 days pre-LMP, through the first day of the last menstrual period (LMP) and up to and including the end of pregnancy. Identification of pregnancy will be via postmarketed reporting through Amgen's Global Safety Database.

Other Covariate(s): Other covariates will be included which pertain to maternal information, exposure and pregnancy and delivery. Maternal covariates include demographic information for the mother, pregnancy history; medical history; other relevant history that may impact the pregnancy (family history, mother's occupation). Variables related to exposure include current medication and dates of use (prescription and over-the-counter [OTC]); and occurrence and dates of current pregnancy complications. Characteristics of pregnancy and delivery such as maternal conditions, birth information, delivery details, and newborn complications.

- Study Sample Size

Sample size will not be pre-determined. This is a descriptive study which will identify the number of pregnant women exposed to Repatha through the Amgen Global Safety Database.

- Data Analysis

These cases constitute an exposed case series, thus line listings of pregnancy and maternal complications, pregnancy outcomes, infant outcomes and adverse events will be summarized along with tabulations of the numbers and frequencies of events by category of report: numbers who did not provide consent for follow-up, timing of exposure (pre-LMP, which trimester), and indication for use of the medication.

Collection of exposure and outcome information in this group provides additional evidence on the safety of Repatha use during pregnancy. The denominator is the number of pregnant women exposed to Repatha during pregnancy and the numerator is the number with the outcome. The proportion at birth with adverse events including complications, medical problems or congenital anomalies will be estimated in infants of women exposed to Repatha during pregnancy. The proportion of infants with adverse events observed at 6 months and 12 months of age will be estimated. The proportion of mothers who have received Repatha at any time during the pregnancy with pregnancy and maternal complications and adverse events will be summarized. Corresponding 95% confidence intervals will also be presented.

To assess effects on the developing fetus and neonate in women exposed to Repatha during pregnancy, the proportion with spontaneous abortions, elective abortions, fetal deaths/stillbirths and premature delivery will be presented, along with corresponding 95% confidence intervals

If the available safety information relevant to exposure during pregnancy represents a safety signal, the signal will be further evaluated through the Amgen safety governance structure and, if deemed necessary, escalated for consideration of changes to the Reference Safety Information (eg, United States Prescribing Information [USPI]) as well as other forms of risk communication (eg, Dear Healthcare Provider Letters).

5. Amendments and Updates

None.

6. Rationale and Background

In the United States (US), Repatha is indicated: (1) In adults with established cardiovascular disease to reduce the risk of MI, stroke, and coronary revascularization; (2) As an adjunct to diet, alone or in combination with other lipid-lowering therapies (eg, statins, ezetimibe), for the treatment of adults with primary hyperlipidemia (including HeFH) to reduce LDL-C; and (3) as an adjunct to diet and other LDL-C-lowering

therapies (eg, statins, ezetimibe, low-density lipoprotein (LDL) apheresis) for the treatment of patients with HoFH who require additional lowering of LDL-C (revised USPI, February 2019). There are no data available on use of Repatha in pregnant women to inform a drug-associated risk. In Section 8.1, the USPI for Repatha states to “consider the benefits and risks of REPATHA and possible risks to the fetus before prescribing REPATHA to pregnant women.” Information on the pregnancy exposure registry was added to Section 8.1 of the USPI as well as to the US Patient Package Insert (February 2019).

6.1 Diseases and Therapeutic Area

A serine protease expressed predominantly in the liver, kidney, and intestine (Seidah et al, 2003), proprotein convertase subtilisin kexin type 9 (PCSK9), plays an important role in the recycling and regulation of the LDL receptor (Horton et al, 2007; Brown and Goldstein, 2006). PCSK9 acts via direct binding to the LDL receptor, resulting in post-translational down-regulation of receptor expression on the hepatic cell surface. This in turn leads to increased levels of circulating LDL-C. Repatha is a fully human monoclonal IgG2 that binds specifically to human PCSK9 and prevents the interaction of PCSK9 with the LDL receptor, thus lowering plasma LDL-C levels.

Based on modality, mechanism of action, published human data, and nonclinical studies, safety issues during pregnancy are not expected with Repatha exposure. As a therapeutic monoclonal antibody, placental transfer during organogenesis in humans is likely to be low (DeSesso et al, 2012; ICH, 2009). Further, the conceptus derives at least 80% of its cholesterol needs from endogenous synthesis rather than from the maternal circulation (Bartels et al, 2012; Woollett, 2005). Independence from maternal sterol status indicates that normal fetal development would not be expected to be affected by the cholesterol lowering properties of Repatha which are independent of effects on cholesterol synthesis. Across multiple species including humans, the rates of cholesterol synthesis in the fetus are much greater than in the adult (Dietschy et al, 1993). Consistent with this, low maternal cholesterol is not causally associated with adverse birth outcomes. Whether mediated by dietary intervention or by genetic mutations, normal embryo-fetal development has been observed in children born to mothers with low cholesterol throughout pregnancy (Homanics et al, 1993; McMurry et al, 1981; Connor et al, 1978).

Moreover, in animal and reproduction studies, there were no effects on pregnancy or neonatal/infant development when monkeys were subcutaneously administered Repatha

from organogenesis through parturition at exposures up to 12 times the exposure at the maximal recommended human dose of 420 mg every month. However, in a similar study with another drug in the PCSK9 inhibitor antibody class, humoral immune suppression was observed in infant monkeys exposed to that drug in utero at all doses. The exposures where immune suppression occurred in infant monkeys were greater than those expected clinically. No assessment for immune suppression was conducted with Repatha in infant monkeys (Amgen, 2016).

6.2 Rationale

This study is being conducted to address a FDA postmarketing requirement to conduct a prospective and retrospective observational study of pregnant women exposed to Repatha to evaluate fetal and infant outcomes through the first year of life. This study will estimate the risk of pregnancy and maternal complications, adverse events on the developing fetus and neonate, and adverse events on the infant through the first year of life using data from pre-existing reports within Amgen's Global Safety Database.

6.3 Statistical Inference (Estimation or Hypothesis)

This is an estimation study. No formal hypothesis will be tested.

7. Research Question and Objectives

7.1 Primary

Among women exposed to Repatha during pregnancy, to estimate the proportion of:

1. Pregnancy and maternal complications
2. Adverse events in the developing fetus and neonate
3. And among their infants, adverse events for the first year of life.

8. Research Methods

8.1 Study Design

This is a worldwide, single-arm, observational case series that collects prospective and retrospective data in women exposed to Repatha during pregnancy to estimate the proportion of pregnancy and maternal complications, adverse events in the developing fetus and neonate, and adverse events in the infant in all exposed pregnancies. Infant outcomes will be assessed through the first year of life.

8.2 Setting and Study Population

The study population includes women worldwide exposed to Repatha during pregnancy that consented for pregnancy and infant follow-up. Case information will be obtained through the Amgen Global Safety Database and other post marketing sources which

include: spontaneous (including regulatory authority and literature), solicited (ie, patient support programs and market research), and postmarketing non-interventional studies.

8.2.1 Study Period

The study is retrospective and prospective. Retrospectively, data will be extracted from pre-existing postmarketing reports obtained from Amgen's Global Safety Database for women exposed to Repatha during pregnancy and their infants between July 2015 and the approval date of this protocol. Prospectively, from approval date of this protocol through July 2025, secondary data from postmarketing reports will be analyzed for women who have been exposed to Repatha during their pregnancy and among their infants.

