8.2.2 Patient Eligibility

8.2.2.1 Inclusion Criteria

Women exposed to Repatha during pregnancy and their infants through the first year of life who consent to provide their information to Amgen.

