As per Amgen's due diligence process, upon notification of a Repatha exposure during pregnancy (with or without an adverse event), Amgen Global Patient Safety follows up with the reporter to request informed consent to obtain pregnancy and infant health information from the mother. Follow-up will be performed as per Amgen's routine pharmacovigilance process at predefined intervals and adjusted accordingly depending on whether the mother is pregnant or has already delivered. Information requested may include, but is not limited to, alternate contact information for the mother, such as contact information of a close relative or friend, pregnancy/delivery details, medical history, laboratory and diagnostic tests, and HCP names. The process includes a set number of follow-up attempts over predefined intervals (post birth, when the infant is 6 months and 12 months). If there is no response to the follow-up attempts the due diligence process is complete and the case is considered lost to follow-up. An exception to this process is when the reporter explicitly states they are not prepared to provide any further information, did not provide consent to follow-up, or refused to provide any additional information about the pregnancy or infant. If this occurs, follow-up is not conducted.

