8.7.2.2 Missing or Incomplete Data and Lost to Follow-up

We are describing pregnancy and infant outcomes among women exposed to Repatha during pregnancy. We are not assessing associations, so missing or incomplete data will not cause bias. However, it may affect the accuracy of our reporting on the description of the population and outcomes. Due to self-report, women with adverse events may be more likely to report than women without. This may result in overestimation of the proportion of exposed pregnancies with adverse outcomes.

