8.7.2.3.3 Analysis of the Primary, Secondary, and Exploratory Endpoint(s)

All analyses will be descriptive. These cases constitute a case series, thus line listings of pregnancy and maternal complications, pregnancy outcomes, infant outcomes and adverse events will be summarized along with tabulations of the numbers and frequencies of events by category of report: numbers who did not provide consent for follow-up, timing of exposure (first, second, or third trimester), and indication for use of the medication. Collection of exposure and outcome information in this group provides additional evidence on the safety of Repatha use during pregnancy. The denominator is the number of pregnant women exposed to Repatha during pregnancy and the numerator is the number with the outcome.

The proportion of infants with adverse events including complications, medical problems or congenital anomalies at birth will be assessed in infants of women exposed to Repatha during pregnancy with corresponding 95% confidence intervals. The proportion of infants with adverse events at 6 months and 12 months of age will be assessed. All adverse events among mothers who have received Repatha at any time during the pregnancy will be summarized including the proportion with pregnancy and maternal complications. To assess events in the developing fetus and neonate in women exposed to Repatha during pregnancy, the proportion of pregnancies resulting in spontaneous abortions, elective abortions, fetal death/ stillbirths and premature delivery will be presented, along with corresponding 95% confidence.

If the available safety information relevant to exposure during pregnancy represents a safety signal, the signal will be further evaluated through the Amgen safety governance structure and, if deemed necessary, escalated for consideration of changes to the Reference Safety Information (eg, USPI) as well as other forms of risk communication (eg, Dear Healthcare Provider Letters).

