8.7.2.4.2 Stratified Analysis

Not applicable.

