Appendix E. 6- and 12-month Infant Questionnaire

Mother Safety Database #	
Infant Safety Database #	

SIX AND TWELVE MONTH
INFANT QUESTIONNAIRE

From: {Title} {First Name} {Last Name} {Company Name} {Country}	[today]
To:[reporter_first_name:corresp_contact] [reporter_last_name:corresp_contact]	

Event: Pregnancy	Product: [product_name]:[1]
AER#: [case_id]	Reply Due By: {Due Date}

Dear [reporter_first_name:corresp_contact] [reporter_last_name:corresp_contact],

Thank you for reporting your [patient_initials] pregnancy while on [product_name:first_suspect] ([generic_name:first_suspect]) therapy. Please send the completed questionnaire with requested information to the address, email or fax below.

Kindly note the following attachments:

- **SIX AND TWELVE MONTH INFANT QUESTIONNAIRE**

Respectfully Yours,

{Title} {First Name} {Last Name}
{Company Name} {Country}
Email: {email}
Fax: {fax}
Phone: {phone}

SIX AND TWELVE MONTH INFANT QUESTIONNAIRE

Mother Safety Database #

Infant Safety Database #

You may return completed form to Amgen Office Fax or Email:

Section 1 – Reporter Information

Reporter: Mother Father Health Care Professional (HCP) Other _____

Section 2 – Infant Healthcare Provider (HCP) Information

May Amgen contact the HCP for medical information regarding your child? Yes No

If yes, please provide contact information:

Name _____ Phone () _____ Fax () _____

Email _____ Address _____ City _____

State/Province _____ Zip/Postal Code _____ Country _____

Section 3 – Infant Medical Health Information

List any other medications/drugs (include vitamins and over-the-counter medications taken by the child)

Medications/Drugs	Dose	Route (e.g. oral, subcutaneous)	Frequency (e.g. daily, weekly)	Date Drug Started (dd/mm/yy)	Date Drug Stopped (dd/mm/yy)	Indication for Treatment

Has the infant had any abnormal screening tests? Yes No If yes, please explain:

Has the infant followed growth curves and developmental milestones as expected for chronological age?

Yes No If no, please explain:

Has the infant had any illnesses or persistent health problems? Yes No If yes, please explain:

Section 4 – Reporter Signature

Signature of person completing questionnaire: _____ Date: _____

Please print name: _____ Title and specialty if HCP _____

Approval Signatures

Document Name: Protocol-Published Original Evolocumab 20200408

Document Description:

Document Number: CLIN-000272100

Approval Date: 16 Jul 2021

Type of Study Protocol: Original

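### Retrospective and prospective are split at the protocol approval date, not by whether the outcome was known at first report, and all reports are pooled, so outcome-selected reports can inflate the primary proportions

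*Protocol*

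**What the plan says.** Protocol Section 8.2.1, repeated in the abstract (Section 4), divides the study by calendar. The retrospective part covers the time "between July 2015 and the approval date of this protocol". For the rest: "Prospectively, from approval date of this protocol through July 2025, secondary data from postmarketing reports will be analyzed". The approval page at the end of the document carries "Approval Date: 16 Jul 2021", so that is the dividing date.

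Eligibility in Section 8.2.2.1 rests on exposure and consent alone: "Women exposed to Repatha during pregnancy and their infants through the first year of life who consent to provide their information to Amgen". Section 8.2.2.2 lists no exclusions. Section 8.2 admits spontaneous, regulatory, literature, solicited and non-interventional-study reports.

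Section 8.7.2.3.3 sets one denominator, all exposed pregnant women. It tabulates by consent status and by "timing of exposure (first, second, or third trimester), and indication for use of the medication". Section 8.7.2.4.2 on stratified analysis reads "Not applicable", as do the neighbouring sections on sensitivity, subgroup and bias analyses. The comment to checklist Section 10 (Appendix B) says no sensitivity analyses will be done.

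On selection, Section 8.7.2.2 says that "women with adverse events may be more likely to report than women without" and that overestimation may follow. Section 8.7.6 states that the analysis has no limitations, and the comment to checklist Section 12 says that bias will not affect the results.

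**The concern.** What matters in a pregnancy case series is whether the outcome was known when the case was first notified. A woman who reports at week 8 and is followed to delivery was not selected on her outcome, whether she called in 2018 or in 2023. A woman who first reports after a loss or an affected birth may have reported because of it. The calendar labels put the 2018 caller in the retrospective part and a 2023 report of a loss that has already happened in the prospective part. Tabulating by the protocol's own labels would therefore not isolate the outcome-selected reports.

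The protocol expects such reports. Section 8.4 adjusts follow-up "depending on whether the mother is pregnant or has already delivered", and the initial questionnaire (Appendix C, Section 7) already asks for the date on which the pregnancy ended and its outcome.

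The sole objective is to estimate proportions. Section 8.7.2.3.3 sends any apparent signal to safety governance, with possible label changes. A proportion that mixes the two kinds of report estimates the risk in neither, and its confidence interval reflects sampling error only.

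**Working it through.** The protocol gives no sample size, expected proportion or share of outcome-known reports, so there is no figure of its own to reproduce. The calculation shows the mechanism under assumed inputs.

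Inputs, all assumed:
- p: true proportion with the adverse outcome
- s: share of reports whose outcome was known at first report
- k: how many times as likely an affected pregnancy is to be reported as an unaffected one, once the outcome is known

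Only the direction, k above 1, comes from the protocol (Section 8.7.2.2).

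**Step 1.** Proportion among outcome-known reports: kp / (kp + 1 − p). With p = 0.15:
- k = 1.5: 0.225 / 1.075 = 20.9%
- k = 2: 0.30 / 1.15 = 26.1%
- k = 3: 0.45 / 1.30 = 34.6%
- k = 5: 0.75 / 1.60 = 46.9%

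**Step 2.** Pooled proportion: (1 − s)p + s × (result of step 1). With s = 0.5:
- k = 1.5: 0.075 + 0.105 = 18.0%
- k = 2: 0.075 + 0.130 = 20.5%
- k = 3: 0.075 + 0.173 = 24.8%
- k = 5: 0.075 + 0.234 = 30.9%, about 2.06 times the truth

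**Step 3.** Dependence on s and p:

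| True p | s | k = 2 | k = 5 |
|---|---|---|---|
| 3% | 25% | 3.7% | 5.6% |
| 3% | 50% | 4.4% | 8.2% |
| 3% | 75% | 5.1% | 10.8% |
| 10% | 25% | 12.0% | 16.4% |
| 10% | 50% | 14.1% | 22.9% |
| 10% | 75% | 16.1% | 29.3% |
| 15% | 25% | 17.8% | 23.0% |
| 15% | 50% | 20.5% | 30.9% |
| 15% | 75% | 23.3% | 38.9% |

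With s = 0 or k = 1 the pooled figure equals p.

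**Step 4.** Coverage of a nominal 95% interval for p. A Clopper-Pearson interval is assumed, and the count is the sum of two binomials, one for each kind of report. With p = 10%, s = 50% and 100 reports, coverage is 76.2% for k = 2 and 5.2% for k = 5. With 200 reports and k = 2 it falls to 61.5%. More reports narrow the interval around the wrong value.

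**Step 5.** Effect of separating the reports, for p = 10%, s = 50%, k = 5 and 100 reports. The pooled expectation, rounded, is 23/100 (95% CI 15.2% to 32.5%), which excludes 10%. The outcome-unknown half gives 5/50 (3.3% to 21.8%), which includes it. The restricted interval is wider, 18.5 against 17.3 percentage points, although its estimate is much smaller.

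**The case against.** Several points on the other side have weight.

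- **The calendar split is only an extraction label.** It stands under Study Period and no analysis uses it. That is right: the inflation comes from the pooling. The label matters because it takes the words that should mark outcome-unknown cases and gives them another meaning.
- **The bias is disclosed and the study is descriptive.** Section 8.7.2.2 gives its direction, and line listings are planned. A reader might infer that a drug effect could never be told from reporting selection. The documents do not support that, since the disclosure and the listings give some warning. But a descriptive proportion with an interval is still an estimate, and Section 8.7.6 and checklist Section 12 contradict the disclosure.
- **Not every proportion need be affected.** A reader might infer that all the primary proportions are distorted. A report received eight weeks after delivery is outcome-known for the birth but not for events at 12 months. Defects found in fetal losses are already set apart (Section 8.7.5.1.1). Nothing keeps outcome-known reports out, but neither presence nor size is shown for each outcome.
- **Consent limits entry.** Published or regulator-forwarded losses may have no consenting mother, so it cannot be assumed that they all enter. A spontaneous report from a consenting woman is enough for the point.
- **The analysis plan could add a breakdown.** The protocol tabulates by exposure timing although it calls stratification not applicable, so a further table is possible. The single denominator for the primary proportions is nonetheless fixed in the protocol.
- **The FDA requirement covers both kinds of data.** It does, as Sections 4 and 6.2 state, but neither section requires that they be pooled in one proportion.

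**Conclusion.** The point holds. The plan defines retrospective and prospective by a date unrelated to selection, pools all reports in one denominator, provides no analysis that separates outcome-known reports, and both concedes and denies the resulting bias. As written it can give upwardly biased primary proportions with intervals that take no account of this.

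The direction is the protocol's own; the size is unknown. The range of 18.0% to 30.9% against a true 15% rests on an assumed half of reports being outcome-known and on k from 1.5 to 5. It shrinks to nothing as either the share goes to zero or k goes to 1.

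**What to change.** - **Section 8.2.1, and the abstract to match:** classify each case outcome by outcome. It is prospective if first reported to the sponsor before that outcome was known and retrospective otherwise, whatever the calendar date. For pregnancy and birth outcomes it must also have been reported before a prenatal abnormality was known. Infant events at 6 and 12 months are classified by whether those events were known at first report, so that a case first reported after birth is not dropped from them without reason.
- **Section 8.7.2.3.3:** base the primary proportions and 95% confidence intervals on the prospective cases. Show retrospective cases in separate tabulations and line listings, with the pooled figure as supportive.
- **Section 8.7.2.4.2:** replace the not-applicable entry with this split.
- **Section 8.7.6 and checklist Section 12:** bring them into line with Section 8.7.2.2.

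The flags can be derived from the date of receipt, the pregnancy end date, pregnancy status at first contact and the narrative. The date on which a prenatal abnormality became known may need reading from the case, because the fetal-test question in Appendix C has no date field. No case is lost from the report.

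The cost is a smaller primary set with wider intervals, and an amendment that needs FDA agreement under Section 11.1. The change does not cure differential consent, differential retention or missed early losses, which should remain as stated limitations.
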